9.5.1.10.4 Serious Adverse Events

An SAE is any untoward medical occurrence that, at any dose, meets one of the following criteria:

- Results in death
- Is life-threatening (i.e., the subject was at immediate risk of death from the AE as it occurred; this does not include an event that, had it occurred in a more severe form or was allowed to continue, might have caused death)
- Requires inpatient hospitalization or prolongation of existing hospitalization
- Results in persistent or significant disability or incapacity
- Is a congenital anomaly or birth defect (in the child of a subject who was exposed to the study drug)

Other important medical events that may not be immediately life-threatening or result in death or hospitalization but, when based on appropriate medical judgment, may jeopardize the subject or may require intervention to prevent one of the outcomes in the definition of an SAE listed above should also be considered SAEs. Medical and scientific judgment should be exercised in deciding whether expedited reporting is appropriate in such situations.

Other events of interest include pregnancy or exposure to study drug through breastfeeding; AEs associated with study drug overdose, misuse, abuse, or medication error; and any treatment-emergent significant laboratory abnormality. These events of interest are to be captured using the SAE procedures but are to be considered SAEs only if they meet one of the above criteria. All AEs associated with events of interest are to be reported on the CRF whether or not they meet the criteria for SAEs.

The following hospitalizations are not considered to be SAEs because there is no AE (i.e., there is no untoward medical occurrence) associated with the hospitalization:

- Hospitalizations for respite care
- Planned hospitalizations required by the protocol
- Hospitalization planned before informed consent (where the condition requiring the hospitalization has not changed after study drug administration)
- Hospitalization for administration of study drug or insertion of access for administration of study drug
- Hospitalization for routine maintenance of a device (e.g., battery replacement) that was in place before study entry

9.5.2 Efficacy Assessments

9.5.2.1 11-Point Bladder Pain and Urgency Scales

The 11-point bladder pain and urgency NRSs are provided in [Appendix 3](#). The 11-point pain and urgency scales are two scales that are used to assess bladder pain, the primary endpoint of this study, and urinary urgency. The subject will be asked to circle the number, from 0 to 10, that best describes the symptom the subject is feeling “right now.” The 11-point bladder pain and urgency scales will be explained to the

subject by the investigator or designee prior to the subject completing the questionnaire. Guideline scripts for the 11-point pain and urgency scales are provided in [Appendix 4](#).

9.5.2.2 Patient Overall Rating of Improvement of Symptoms Questionnaire

The PORIS questionnaire is provided in [Appendix 5](#). It comprises three questions that ask the subject to report the overall change in pain and urgency *now* as compared with *before* study drug administration. The choices are the same for each symptom: worse, no better (0% improvement), slightly improved (25% improvement), moderately improved (50% improvement), greatly improved (75% improvement), and symptoms gone (100% improvement). The PORIS questionnaire will be explained to each subject by the investigator or designee prior to the subject completing the questionnaire. A guideline script for the PORIS questionnaire is provided in [Appendix 6](#).

9.5.2.3 24-Hour Pain and Urgency Scale Diary and Urination Log

Each subject will be provided with a set of pain and urgency questionnaires that use the 11-point NRSs that will be recorded by the subject at home after receiving the study medication, until going to bed. Pain measurements will be recorded on-site up to 2 hours after study drug administration [at Time 0, 30 minutes (\pm 5 minutes) and 1 hour (\pm 5 minutes), 2 hours (\pm 10 minutes)], and at home at 4 hours (\pm 30 minutes), 6 hours (\pm 30 minutes), 8 hours (\pm 30 minutes), 10 hours (\pm 30 minutes), and 12 hours (\pm 30 minutes) while the subject is awake. The last set of pain and urgency questionnaires will be completed at 24 hours, and may be completed at the clinic if the subject returns to the clinician's office (Visit 2) at 24 hours (\pm 2 hours) after study drug administration or, at the Investigator's discretion, will be completed at home and returned to the clinic per the Investigator's directions. The site staff will ensure that the proper subject initials and numbers, and study drug administration time are recorded in each subject's diary prior to dispensing them. The diary also contains a urination log. The diary will be explained to each subject by the investigator or designee prior to the subject recording any data in the diary. Site staff will be tasked with placing phone calls to remind each subject to complete the diary at the assigned times, and if the subject has been given permission by the Investigator to not return for Visit 2 to confirm the return of the completed subject diary and answer any follow up questions.

9.5.3 Pharmacokinetic Assessments

9.5.3.1 Lidocaine Concentration

A blood sample will be collected to determine the concentration of lidocaine in the peripheral blood. An initial blood sample will be collected at baseline prior to study drug administration, and a second blood sample will be collected 1 hour (\pm 10 minutes) after administration of the study drug (i.e., 1 hour after instillation) to determine plasma lidocaine concentrations.

9.5.4 Schedule of Assessments

The schedule of assessments for the study is provided in [Table 4](#).

Table 4. Schedule of Assessments

9.5.5 Appropriate ness of Measurements

All clinical assessments are standard measurements commonly used in studies of IC/BPS.

The safety assessments to be performed in this study (including hematology analyses, blood chemistry tests, urinalysis, and assessment of AEs) are standard evaluations to ensure subject safety.

9.5.6 Reporting of Serious Adverse Events, Pregnancy, and Other Events of Interest

9.5.6.1 Reporting of Serious Adverse Events

All SAEs, regardless of their relationship to study drug, must be reported on a completed SAE form by email or fax as soon as possible to [REDACTED] but should be reported no later than 24 hours from the time the investigator becomes aware of the SAE.

Any death or any life-threatening event should be reported immediately by telephone to [REDACTED] The immediate report should be followed up within 1 business day by emailing or faxing the completed SAE form.

SAEs, regardless of causality assessment, must be collected through the last visit and up to 72 hours after drug administration. All SAEs must be followed to resolution or, if resolution is unlikely, to stabilization. Any SAE judged by the investigator to be related to the study treatment should be reported to the sponsor regardless of the length of time that has passed since study completion.

For urgent safety issues, please ensure all appropriate medical care is administered to the subject, and contact the appropriate study team member listed in the Investigator Study File.

It is very important that the SAE form be filled out as completely as possible at the time of the initial report. This includes the investigator's assessment of causality.

Any follow-up information received about SAEs should be forwarded within 1 business day of its receipt. If the follow-up information changes the investigator's assessment of causality, this should also be noted on the follow-up SAE form.

Preliminary SAE reports should be followed as soon as possible by detailed descriptions of additional information including copies of hospital case reports, autopsy reports, and other documents, if requested by the sponsor.

The investigator must notify the IRB of the occurrence of the SAE, in writing, if required by their institution. A copy of this communication must be forwarded to the sponsor or the contract research organization to be filed in the sponsor's Trial Master File.

9.5.6.2 Reporting of Pregnancy

Any pregnancy in which the estimated date of conception is either before the last visit or within 30 days of study drug administration must be reported to Urgen.

If an adverse outcome of a pregnancy is suspected to be related to study drug exposure, this should be reported, regardless of the length of time that has passed since the exposure to study treatment.

A congenital anomaly, death during the perinatal period, an induced abortion, or a spontaneous abortion are considered to be an SAE and should be reported in the same time frame and in the same format as all other SAEs (see [Section 9.5.6.1](#), Reporting of Serious Adverse Events).

Pregnancies or exposure to study drug through breastfeeding must be reported by fax or email as soon as possible but no later than 1 business day from the date the investigator becomes aware of the pregnancy. The contact information for the reporting of pregnancies and exposure to study drug through breastfeeding is provided in the investigator study file. The Pregnancy Report Form must be used for reporting pregnancies. All pregnancies must be followed to outcome, whenever possible. The outcome of the pregnancy must be reported as soon as possible but no

later than 1 business day from the date the investigator becomes aware of the outcome.

9.5.6.3 Reporting of Other Events of Interest

REPORTING OF ADVERSE EVENTS ASSOCIATED WITH STUDY DRUG OVERDOSE, MISUSE, ABUSE, OR MEDICATION ERROR

AEs associated with study drug overdose, misuse, abuse, and medication error refer to AEs associated with uses of the study drug outside of that specified by the protocol. Overdose, misuse, abuse, and medication error are defined as follows:

Overdose	Accidental or intentional use of the study drug in an amount higher than the protocol-defined dose (If applicable, define the study-specific criteria for overdose that should be applied when determining whether an overdose occurred.)
Misuse	Intentional and inappropriate use of study drug not in accordance with the protocol
Abuse	Sporadic or persistent intentional excessive use of study drug accompanied by harmful physical or psychological effects
Medication error	Any unintentional event that causes or leads to inappropriate study drug use or subject harm while the study drug is in the control of site personnel or the subject

All AEs associated with an overdose should be captured in the Adverse Event CRF. Adverse events associated with overdose, misuse, abuse, or medication error should be reported using the procedures detailed in [Section 9.5.6.1](#), Reporting of Serious Adverse Events even if the AEs do not meet serious criteria. Drug abuse is always to be captured as an AE. If the AE associated with an overdose, misuse, abuse, or medication error does not meet serious criteria, it must still be reported using the SAE form and in an expedited manner; however, the AE should be noted as nonserious on the SAE form and in the Adverse Event CRF.

9.5.6.4 Breaking the Blind

In the case of a medical emergency where the appropriate treatment of the subject requires knowledge of the study treatment given, the investigator may request that the medical monitor break the blind for an individual subject as described in the Study Procedures Manual. In all such cases, the AE necessitating the emergency blind break will be handled as an SAE in accordance with the procedures indicated above. Any broken code will be clearly justified and documented.

9.5.6.5 Regulatory Reporting of Adverse Events

AEs will be reported by the sponsor or a third party acting on behalf of the sponsor to regulatory authorities in compliance with local and regional law and established guidance. The format of these reports will be dictated by the local and regional requirements.

9.5.7 Completion and Discontinuation of Subjects

A subject may elect to discontinue the study at any time for any reason without prejudice. All subjects who discontinue the study are to complete the study's Visit 2 procedures and the follow-up phone call indicated in the schedule of assessments ([Table 4](#)) whenever possible.

The investigator will promptly explain to the subject involved that the study will be discontinued for that subject and provide appropriate medical treatment and other necessary measures for the subject. A subject who has ceased to return for visits will be followed up by mail, phone, or other means to gather information such as the reason for failure to return, the status of treatment compliance, the presence or absence of AEs, and clinical courses of signs and symptoms. This information will be recorded in the CRF.

Subjects who discontinue early from the study will be discontinued for one of these primary reasons: AE(s), lost to follow-up, catheter intolerance, inadequate therapeutic effect, withdrawal of consent, pregnancy, study terminated, or other (to be specified). In addition to the primary reason, the subject may indicate one or more secondary reasons for discontinuation.

9.6 DATA QUALITY ASSURANCE

9.6.1 Monitoring

The study will be monitored by designees of Urgen N.A., Inc. at all stages of study conduct, from inception to completion, in accordance with current GCP. This monitoring will be in the form of site visits and other communication and will include review of original source documents and CRFs. The monitor will notify the investigator prior to conducting any investigational site visit. The frequency of these visits will depend upon the progress of the study, and will include monitoring to assess facilities and equipment, recruiting, record-keeping, protocol adherence, data collection, AE reporting, and other factors.

9.6.2 Investigator's Responsibility

The investigator will retain all study documents required to be maintained (1) for at least 2 years after the date a marketing application is approved for the drug for the indication for which it is being investigated, or (2) if no application is to be filed or if the application is not approved for such indication, until 2 years after the investigation is discontinued and the FDA is notified.

9.7 STATISTICAL METHODS

All statistical analyses, except the interim analysis, will be performed after each study is completed, the database is locked and released, and randomization codes have been released. Statistical analyses will be performed using SAS or other validated statistical software as required. Details of the statistical analyses will be included in a separate statistical analysis plan (SAP).

9.7.1 Statistical and Analytical Plans

The statistical analyses of study data are described in this section. All hypothesis tests will be 2-sided and will use an alpha level of 0.05. Additional details of the analytical plan will be provided in the SAP, which will be finalized before database lock.

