Statistical Methods:	
Sample Size Estimate Sample size estimates were based on a pilot trial of heparin-lidocaine versus lidocaine alone and a prior two-arm study of URG101 versus placebo. The primary efficacy endpoint is SPID-12. The sample size calculation is based on a one-way analysis of variance, comparing SPID-12 from four treatment groups. A target sample size of 180 subjects to be allocated unequally among the four treatment groups as follows: URG101:placebo:lidocaine: heparin at 2:1:2:1 (60 subjects per group and 30 subjects per group). This sample size is sufficient to achieve 90% power to detect a difference between the URG101 and lidocaine groups assuming a treatment effect size of 0.60. The study will also have 90% power to detect a difference between the URG101 and each of the placebo and heparin groups assuming an effect size for these comparisons of 0.75. Once 90 subjects have been enrolled, a blinded interim analysis will take place; and, if required, the number of subjects for the study increased to a maximum of 300 subjects.
 
Description of Analysis Sets: All analyses of the efficacy of URG101 will be performed on the ITT set, which will include all randomized subjects from the investigative phase of the study who receive study drug. These efficacy analyses will compare the treatment groups on the basis of randomized treatment, regardless of the treatment actually received. Primary efficacy and key secondary efficacy analyses will also be conducted on a per protocol set, which will include all subjects in the ITT set who sufficiently comply with the protocol.
 
Safety analyses will be based on the safety analysis set which will include all subjects who receive at least one dose of study drug and have at least one post dose safety assessment in both phases of the study. Safety summaries will be produced based on study treatment actually received.

CLINICAL PROTOCOL SYNOPSIS (continued)

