9.7.1.14 Efficacy Analyses

All SPID endpoints will be calculated using Simpson's trapezoidal rule. SPID will be calculated as follows, where n is the total number of time points within the time period with non-missing imputed PID values:

If multiple scores are recorded at the same date and time, the most conservative PI scores (highest) will be used.

Primary Efficacy Analyses

The primary efficacy analyses will be performed on the intent-to-treat set. As a sensitivity analysis, the primary efficacy analysis will also be performed on the PP set. Primary efficacy analyses will also be conducted on the per protocol set, which will include all subjects in the ITT set who sufficiently comply with the protocol.

The primary efficacy endpoint will be compared between the URG101 group and the lidocaine, heparin, and placebo groups using an analysis of covariance model including factors for site and randomized treatment assignment; baseline pain will be added to the model as a covariate. Pairwise comparisons of least squares means between URG 101 and the two active treatment arms, as well as the placebo arm, will be performed. The probability values will be derived using the contrast statement from the model. If the p-value associated with these comparisons is < 0.05 in favor of URG101, the primary aim of the trial will be confirmed.

Sites with small numbers of patients enrolled may be pooled for analysis. The method used to determine pooling will be specified in the statistical analysis plan and any pooling will be finalized and documented prior to database lock and unblinding.

Secondary Efficacy Analyses

Analyses of the secondary endpoints relating to changes in the pain and urgency NRS will be performed using analysis of covariance models similar to those used for the primary efficacy endpoint. The ITT set will be used. Nonparametric methodology in exploratory analyses may be used to supplement the parametric analyses.

Treatment differences based on the PORIS questionnaire, Question 3, will be analyzed by pairwise Cochran-Mantel-Haenszel Tests based on $\geq 50\%$ improvement of symptoms.

Time to first pain medication use will be analyzed using Kaplan-Meier methodolgy. Log-rank tests will be used to compare the treament groups.

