9.7.4 Interim Analysis

Re-estimation of the Sample Size

The two possible types of interactions are defined as being either **quantitative** or **qualitative**. A quantitative interaction exists where the relationship of the treatment groups are consistent across the sites, moving in the same direction, but at different magnitudes. A qualitative interaction is much more serious and exists where one treatment group shows a positive effect of the study medication at certain sites, and the other sites show a negative effect of the same study treatment. In most clinical studies, if an interaction is present between site and treatment, there will be a quantitative interaction where the effect size at some sites is greater than at other

sites, but all sites have a positive effect size for the active treatment. Qualitative interactions require additional investigation because of the mixed signals on the effect of a study treatment by study site.

In order to minimize the impact of a small sample effect, for the purposes of the interim analysis, the smaller study sites will be merged to form a pseudo-site. In this way a possible aberration in outcomes that might arise from small samples due to over or under representation of patients with characteristics that may either increase or decrease study results will have a diminished impact on the sample size recalculation.

[figure not shown]

10

2

[REDACTED] : [REDACTED] : [REDACTED]

W

The IDMC will make one of following non-binding recommendations to the sponsor:

- Continue enrolling patients to the pre-specified target sample size
- Continue enrolling patients to a sample size that exceeds the pre-specified target sample size but \leq the maximum sample size
- Stop enrolling patients based on futility

The instructions from the IDMC for the sample size adjustment will be described in detail in the IDMC Charter. An alpha level adjustment will not be necessary for the

procedure described below if the conditional power for the primary endpoint is > 39%.

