9.7.6 Procedure for Revising the Statistical Analysis Plan

If the SAP requires revision after finalization, the sponsor will determine how the revision impacts the study and how the revision should be implemented. The details of the revision will be documented and described in the clinical study report.

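### The SAP deadline is database lock, so the analysis details still open may be settled after the unblinded interim at about 90 subjects and after the sponsor has a sample size recommendation

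*Combined protocol and SAP*

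**What the plan says.** Section 9.7 places the details of the analysis in a separate SAP, and 9.7.1 gives its deadline: "Additional details of the analytical plan will be provided in the SAP, which will be finalized before database lock".

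The interim comes earlier. Sections 9.1.6 and 9.7.3 place it at about 90 subjects (50%) and make it unblinded to the IDMC; the sample size paragraph of the synopsis calls it blinded. Under 9.7.4 the IDMC gives the sponsor one of three non-binding recommendations. One is to "Continue enrolling patients to a sample size that exceeds the pre-specified target sample size", up to the maximum, which is 300. The adjustment rule is left to the IDMC Charter, and part of 9.7.4 is redacted or not shown.

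Two deferred items carry a second condition. On sites, 9.7.1.14 leaves the pooling method to the SAP and says that "any pooling will be finalized and documented prior to database lock and unblinding". Section 9.7.1.5 likewise ties the per-protocol evaluability details to both lock and treatment unblinding. Neither section says whether unblinding includes the IDMC's look.

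If a finalised SAP is revised, 9.7.6 says that "the sponsor will determine how the revision impacts the study and how the revision should be implemented", with the details documented in the study report.

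**The concern.** The usual safeguard is that analysis choices are fixed before anyone who could influence them can learn from unblinded outcomes. Here the first unblinded use of outcomes is the interim, and the sponsor must see the recommendation in order to act on it. A SAP completed between that point and database lock would comply with 9.7.1, yet it could be written by people who know whether the trial was enlarged, left alone or judged futile.

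At stake is the claim that the primary comparison was fully pre-specified. Site in the model and the imputation rule both enter the primary SPID-12 analysis, so choosing between two written alternatives after the interim could move the primary p-value. Neither the analysis nor its timing would look wrong in the study report, because 9.7.6 does not ask for changes to be dated against the interim or for the planned analysis to be kept beside the revised one.

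**Working it through.** **1. What is fixed and what is open**

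| Item | Where | Status |
|---|---|---|
| Primary endpoint SPID-12 | Synopsis, 9.7.1.1 | Fixed (8.1 keeps a sentence letting the IDMC choose it from a run-in; to be reconciled) |
| ITT set, ANCOVA with baseline pain, pairwise contrasts | Synopsis, 9.7.1.14 | Fixed |
| Significance level | 9.7.1: "All hypothesis tests will be 2-sided and will use an alpha level of 0.05" | Fixed |
| Site in the model | Absent in the synopsis, present in 9.7.1.14 | Conflict |
| Imputation for withdrawals | LOCF in the synopsis, baseline carried forward in 9.7.2.1 | Conflict |
| Site-pooling method | 9.7.1.14 | Deferred to the SAP |
| Per-protocol criteria | Two missing-data exclusions in 9.7.2.2; the rest deferred in 9.7.1.5 | Partly open |

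**2. The plan's own figures**

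The synopsis gives "90% power to detect a difference between the URG101 and lidocaine groups assuming a treatment effect size of 0.60", and the same power against "each of the placebo and heparin groups assuming an effect size for these comparisons of 0.75", with allocation "2:1:2:1 (60 subjects per group and 30 subjects per group". By the normal approximation, power = Φ(d/√(1/n₁ + 1/n₂) − 1.96):

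- Lidocaine, 60 v 60: 0.60/0.1826 = 3.286, so Φ(1.326) = 90.8%.
- Placebo or heparin, 60 v 30: 0.75/0.2236 = 3.354, so Φ(1.394) = 91.8%.

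Both agree with the stated 90%.

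**3. How much a new N could disclose**

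The documents give the look at 90, the target of 180, the cap of 300 and the 90% power target. I assume that URG101 v lidocaine drives the decision (30 v 30 at the look, by 2:1:2:1), that N is set exactly to reach 90% conditional power (CP), and a form for CP. With interim statistic z, the interim-trend form is

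CP(N) = 1 − Φ[(1.96√N − z√90)/√(N − 90) − z√((N − 90)/90)].

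At N = 180 this becomes 1 − Φ(2.772 − 2z).

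*Check against the 39% threshold.* Raising N to 300 without adjusting alpha requires [√(210/90)(1.96√180 − z√90) + z√90]/√300 ≤ 1.96. Equality falls at z = 1.243, where CP at 180 is 38.7%. That matches the stated 39%, which suggests a trend-based rule but does not prove one.

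*Inversion.* Solve CP(N) = 0.90 for z, then d = z√(2/30). For N = 240 and z = 1.821: (30.364 − 17.275)/12.247 − 2.351 = −1.282, so CP = 0.90 and d = 0.470. The design-effect form replaces the last term by θ√(N − 90), with θ = 0.60/(√(2/30)·√90) = 0.245. For N = 240 that gives z = 0.982 and d = 0.254.

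| Recommended N | Interim-trend rule: z (d) | Design-effect rule: z (d) |
|---|---|---|
| 181 | 2.023 (0.52) | 1.719 (0.44) |
| 200 | 1.952 (0.50) | 1.498 (0.39) |
| 240 | 1.821 (0.47) | 0.982 (0.25) |
| 280 | 1.710 (0.44) | 0.413 (0.11) |
| 299 | 1.663 (0.43) | 0.129 (0.03) |

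Under the trend rule with increases only above 39% CP, N = 300 gives CP between 39% and 71% (z 1.246 to 1.661, d 0.32 to 0.43). N = 180 means either d of about 0.52 or more, or d of about 0.32 or less.

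*How often each occurs.* Take z as normal with mean d/√(2/30) and variance 1. An intermediate N needs z between 1.661 and 2.027.

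| True d | N 181–299 | N = 300 | N not increased |
|---|---|---|---|
| 0 | 2.7% | 5.8% | 91.5% |
| 0.3 | 11.5% | 15.7% | 72.8% |
| 0.4 | 13.9% | 16.3% | 69.8% |
| 0.5 | 14.5% | 14.6% | 70.9% |
| 0.6 | 13.0% | 11.3% | 75.8% |

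**The case against.** The strongest reply is that the protocol already carries the analysis that matters, that 9.7.1 defers only further detail, and that changing the protocol text requires an approved amendment under 10.1. Only the IDMC has the unblinded scores; its members are independent of study personnel, and its communication is governed by its charter. Database lock is a latest date, so the SAP may well be signed earlier. All of this stands, and it confines the point to the open items in the table above.

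A reader might go further and infer that the recommended N reveals the interim effect to the sponsor. The documents do not support that. The visible text does not say which of the three comparisons drives conditional power, whether the interim trend or the design effect is used, or whether N is exact or stepped. The two rules read the same N = 280 as 0.44 SD or 0.11 SD. Even under the trend rule, an intermediate N has a chance of only about 3% to 15% across true effects of 0 to 0.6.

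A reader might also infer that pooling and the per-protocol criteria are tied to database lock alone. They are not, because both sections add unblinding. But each pairs it with lock, and 9.7 releases the randomisation codes after lock with the interim as an exception, so the condition may mean only end-of-study unblinding.

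Finally, one might claim that the interim and final statistics differ, which would undercut the 39% argument. Section 9.7.4 does merge small sites for the interim while final pooling is undecided, but the interim statistic itself is not visible, so this cannot be tested.

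**Conclusion.** The point holds as a gap in timing. The plan permits the remaining analysis details to be settled after the IDMC's unblinded look and after the sponsor has the recommendation. Two of those details, site in the model and imputation for withdrawals, bear directly on the primary analysis and are written two ways. This follows from the text and needs no assumption about the re-estimation rule.

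The size of any information leak is not established. The ranges above rest on an assumed driving comparison, an exact N and one of two assumed rules. Nor can any inflation of type I error be quantified from the documents. The separate SAP and the IDMC Charter are not reproduced, so an earlier SAP date may exist. This is an inexpensive improvement that should be made, and it does not show that the trial's primary test is compromised.

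**What to change.** - **9.7.1:** replace the database-lock deadline with *before the IDMC receives unblinded data for the 90-subject interim*. The primary model (including whether site is in it), the imputation rules, the site-pooling algorithm and the per-protocol criteria should be signed and dated by then.
- **9.7.1.5 and 9.7.1.14:** state that unblinding includes the interim.
- **9.7.6:** require any later change to be dated relative to the interim and reported alongside the originally planned analysis.

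The cost is that SAP work is brought forward. Sample size, power, alpha and data collection do not change.
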